6.3.5. Multiple Assessments

In general, if multiple valid observations exist in the window of an analysis visit, the record to be included in the summary and analyses will be chosen on the following basis, unless otherwise specified:

- The record closest to the nominal visit

If records are equidistant or distance cannot be determined:

- The latest record

If records have the same date/time:

- The average

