#### **6.4.10.12. Unscheduled Visit**

All sites are allowed at Investigator discretion to conduct either in clinic or remote unscheduled visits for subject safety or unexpected subject medical needs outside of the regular visit schedule. In this case, unscheduled visits are not considered protocol deviations and the Investigator is not required to obtain pre-approval from the Sponsor. Data collected during these visits may include any protocol-specified assessments which will be captured in the clinical database.

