### 8.5.3. [REDACTED]

### 8.5.4. [REDACTED]

## 8.6. Safety Analyses

Safety data, including C-SSRS, will be summarized by treatment received. Summaries will be provided by nominal visit and time point or for the entire treatment period, as appropriate for the type of data. Quantitative data collected at unscheduled times will be listed but will not be included in summaries. Categorical data collected at unscheduled times (e.g., ECG finding categories) will not be included in summaries by time point but will be included in summaries of findings during the entire treatment period.

Safety analyses will be performed using the safety analysis set. Unless specified otherwise there will be no imputation of missing data in safety summaries. Subjects without post baseline measurement (e.g. ECG or vital signs) for a given time point will be excluded from the summary statistic (e.g., denominator of the summary statistic) for that time point.

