6.3.4. Analysis Visit Windows

Assessments that are summarized by visit will be assigned to analysis visits using the following analysis visit windows, without regard to the visit label associated with the assessment in the clinical database.

Table 3: Analysis Visit Windows

Analysis Visit	Analysis Visit Window	
	Start (study day)	Stop (study day)
For endpoints collected at Weeks 1, 2, 3, and 4, including C-SSRS, BSFC-s, OHSA, OHDAS, and vital signs		
Week 1 (study day 7)	2	10
Week 2 (study day 14)	11	17
Week 3 (study day 21)	18	24
Week 4 (study day 28)	25	42
For endpoints collected at Weeks 1 and 3, including ABPM position		
Week 1 (study day 7)	2	14
Week 3 (study day 21)	15	42
For endpoints collected at Weeks 2 and 4, including safety laboratory tests		
Week 2 (study day 14)	2	21
Week 4 (study day 28)	22	42
For endpoints other than PGI-C collected at Week 4, including EQ-5D, NMSS, HADS, UPDRS, PDQ-8, COMPASS-31, UMSARS, and ECG		
Week 4 (study day 28)	15	42
For PGI-C* (collected at Week 4)		
Week 4 (study day 28)	2	42

*All endpoints except PGI-C are also collected on or prior to study day -1. PGI-C, being a change assessment, is collected only at the Week 4 visit or early termination visit.

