9.5. Vital Signs and Weight

The weight and vital sign (HR, systolic and diastolic BP, RR, and body temperature) values and their changes from baseline at each visit will be summarized. At visits when both vital signs and orthostatic standing test are performed, the vital signs (BP and HR) collected after 10 minutes supine and seated from the orthostatic standing test will be used for safety vital signs assessment. Therefore, the summaries will also include body position (supine and seated) as appropriate. The counts and percentages of subjects with vital signs in the following categories will be presented in a vital sign outlier summary. The outliers will be flagged in the listing.

Table 8: Vital Signs Outlier Thresholds

Heart Rate (bpm)	Systolic Blood Pressure (mmHg)	Diastolic Blood Pressure (mmHg)
<40	<85	<45
>110	>160	>100
>120		

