9.6. ECGs

A summary of ECG parameters, including QTcF, PR interval, QT interval, QRS duration, RR, and HR, will be summarized in terms of observed values and change from baseline. The ECG are planned to be collected as triplicates and the average of the measures will be used for the summary.

Outlier Analysis

The number of subjects with absolute ECG values and change from baseline in the ranges shown in [Table 9](#) will be presented in electrocardiogram outlier summary by visit.

In addition, in the same summary, QTcF will also be summarized by the following categories, Normal (males <430, females <450), Borderline (males (≥430, <450); females (≥450, <470)) and Prolonged (males ≥450, females ≥470).

Individual ECG data collected during the study will be presented in a listing. A separate listing of subjects with values of QTcF ≥ 450 msec if male or ≥ 470 msec if female or an increase > 60 msec will be provided, as necessary.

Investigator Assessment of ECG Readings

The investigator's assessment of ECGs as normal, abnormal and clinically significant, or abnormal but not clinically significant will be summarized for baseline and for each visit.

Table 9: ECG Outlier Thresholds

Heart Rate (bpm)	Heart Rate Change from Baseline (bpm)	PR Interval (msec)	PR Percentage Change From Baseline (%)	QRS Interval (msec)	QT _c F (msec)	QT _c F change from Baseline (msec)
>120	≥20	≥ 200	≥ 15	≥ 120	Males:	≤ 30
>130	≥30	≥ 220	≥ 25		< 430	>30, ≤ 60
					≥ 430	> 60
					≥ 450	
					≥ 470	
					≥ 480	
					≥ 500	
					Females:	
					< 450	
					≥ 450	
					≥ 470	
					≥ 480	
					≥ 500	

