9.7. C-SSRS

The C-SSRS is a tool designed to systematically assess and track suicidal AEs (suicidal behavior and suicidal ideation). The strength of this suicide classification system is in its ability to comprehensively identify suicidal events while limiting the over-identification of suicidal behavior. The C-SSRS Baseline/Screening Version will be used at Visit 1 and the C-SSRS Since Last Visit Version will be used at subsequent visits.

Although the Since Last Visit Version of C-SSRS is collected at Visit 2 prior to the 1st dose of the study medication on the following day, it cannot be used as the baseline for C-SSRS assessment. The Baseline/Screening Version of C-SSRS collected at Visit 1 will be used as the baseline. If the Since Last Visit Version of C-SSRS is collected on the same day as the Baseline/Screening Version of C-SSRS, the Since Last Visit Version of C-SSRS doesn't have a valid reference and hence will be excluded from summaries and analyses. But it will be presented in the listing.

The following eleven C-SSRS categories, accepted by FDA as their standard, include five subtypes of suicidal ideation (1-5), five subtypes of suicidal behavior (6-10), and self-injurious behavior without suicidal intent (11). They all have binary responses (yes/no).

1. Wish to be Dead
2. Non-specific Active Suicidal Thoughts

3. Active Suicidal Ideation with Any Methods (Not Plan) without Intent to Act
4. Active Suicidal Ideation with Some Intent to Act, without Specific Plan
5. Active Suicidal Ideation with Specific Plan and Intent
6. Preparatory Acts or Behavior
7. Aborted Attempt
8. Interrupted Attempt
9. Actual Attempt (non-fatal)
10. Completed Suicide
11. Self-injurious behavior without suicidal intent

Frequency counts and percentages will be presented for subjects in each C-SSRS category, as well as subjects with any suicidal ideation (1-5), subjects with any suicidal behavior (6-10), and subjects with any suicidal ideation or behavior (1-10), by treatment group at each visit where the items were collected. The summary of the Baseline/Screening Version of C-SSRS will present separately the assessment over the subject's lifetime and during the last 12 months.

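### Keeping one record per visit window (SAP 6.3.5), with C-SSRS and ECG outliers tabulated only by visit, can leave a positive C-SSRS form or a QTcF outlier out of those tables

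*SAP*

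**What the plan says.** - **Windowing.** SAP 6.3.4 assigns assessments that are summarized by visit to Table 3 windows "without regard to the visit label associated with the assessment in the clinical database". Unscheduled and early-termination (ET) records therefore compete with scheduled ones.
- **Selection.** SAP 6.3.5 is a default: "In general, if multiple valid observations exist in the window of an analysis visit, the record to be included in the summary and analyses" is chosen by closeness to the nominal day ("The record closest to the nominal visit"), then the latest record, then the average if date and time are the same. Other rules may be specified elsewhere. None is visible for multiple post-baseline safety records.
- **C-SSRS.** SAP 9.7 gives counts "by treatment group at each visit where the items were collected". After screening, the Since-Last-Visit version of the form is used.
- **ECG.** SAP 9.6 puts outliers and the QTcF categories in an "electrocardiogram outlier summary by visit". A separate listing covers extreme QTcF.
- **Vital signs.** SAP 9.5 summarizes values and changes at each visit, but of outliers says only: "The counts and percentages of subjects with vital signs in the following categories will be presented in a vital sign outlier summary". Outliers are also flagged in the listing.
- **Protocol 8.6.** Quantitative safety data from unscheduled times are listed and not summarized. Categorical data from unscheduled times stay out of the by-time-point summaries but "will be included in summaries of findings during the entire treatment period".
- **Unscheduled visits.** Protocol 6.4.10.12 allows "unscheduled visits for subject safety or unexpected subject medical needs outside of the regular visit schedule", and any protocol assessment may be done at them.

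**The concern.** Picking the record nearest the nominal day is reasonable for a mean or a change from baseline. It suits safety categories poorly, where the question is whether a subject ever had the finding. No post-baseline any-time or worst-category summary is visible for C-SSRS or ECG, so a finding on an unselected record is missing from the table meant to count it.

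C-SSRS is the sharper case. Each Since-Last-Visit form covers only the interval since the previous one. Two forms in one window cover different days, and setting one aside removes days that no other form covers. SAP 9.7 recognizes that the form depends on its reference point, because it excludes a form that has no valid reference. It has no rule for two valid forms in one window.

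What is at stake is the per-arm count of suicidality findings and QTcF outliers. A count from one record per window can equal an any-time count or fall below it, but never exceed it.

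**Working it through.** The plan states no figure to reproduce. The check applies SAP Table 3 and SAP 6.3.5 day by day.

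**Inputs.** C-SSRS and vital-sign windows (study days): Week 1 = 2–10, Week 2 = 11–17, Week 3 = 18–24, Week 4 = 25–42, with nominal days 7, 14, 21, 28. ECG has one post-baseline window, 15–42, nominal 28. SAP 6.3.1 counts study days from the first dose, normally the day after randomization, so study day = protocol Day − 1. Visits are allowed ±3 days.

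**1. C-SSRS example.** All three forms are Since-Last-Visit.

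| Study day | Visit | Result | Window | Distance to nominal | Selected |
|---|---|---|---|---|---|
| 14 | scheduled | no | Week 2 | 0 | yes |
| 16 | unscheduled | ideation | Week 2 | 2 | no |
| 21 | scheduled | no | Week 3 | 0 | yes |

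The day 21 form looks back to day 16, so no selected form covers days 14 to 16. This assumes that the unscheduled visit counts as the last visit, which is the plain reading of the form's title.

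**2. ECG.** Visit 6 (Day 29 ± 3) falls on study days 25–31, at most 3 days from nominal. An unscheduled ECG on study day 20 is |20 − 28| = 8 days away and loses. Any ECG on study days 15–24 is at least 28 − 24 = 4 days away, so it always loses to a Visit 6 ECG taken within its permitted range. An ET ECG on days 15–42 that is the only post-baseline ECG is kept. An ECG on days 1–14 has no window at all; Table 3 causes that loss, not 6.3.5.

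**3. ET visit as last contact (C-SSRS, vital signs), earlier visits exactly on nominal days.** Of study days 1–28:
- kept: 2–7, 11–14, 18–21, 25–28 = 18 days
- not selected: 8–10, 15–17, 22–24 = 9 days
- no window: day 1

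Check: 18 + 9 + 1 = 28.

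**4. The reverse case.** If scheduled visits run 3 days late, an unscheduled record on days 5–9, 12–16, 19–23 or 26–30 is selected and the scheduled one is set aside.

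**5. Visit 7 (C-SSRS and vital signs).** Day 43 ± 3 is study days 39–45 for a completer who does not enter Study 0170. On days 39–42 the record is at least 39 − 28 = 11 days from nominal and loses to Visit 6. On days 43–45 it has no window (Table 3 again).

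**6. Share of records not selected, under assumed timing (C-SSRS and vital-sign windows only).** Scheduled visits are jittered uniformly and independently by whole days. The unscheduled day is uniform on 2–31, excluding days with a scheduled visit. The ET day is uniform on 2–27; the middle row also excludes days with a scheduled visit.

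| Jitter (± days) | 0 | 1 | 2 | 3 |
|---|---|---|---|---|
| Unscheduled | 100% | 85% | 69% | 54% |
| ET after at least one scheduled visit | 50% | 40% | 31% | 22% |
| ET, all days 2–27 | 35% | 27% | 21% | 15% |

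The zero-jitter ET figures follow from step 3. Days 2–27 are 26 days, and 9/26 = 35%. Days 8–27 without 14 and 21 are 18 days, and 9/18 = 50%.

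**The case against.** **Selection is by distance, not by visit type.** A reader might infer that unscheduled and ET records are removed as such. They are not. A sole or closer record is kept, and step 4 shows a scheduled record being set aside. This stands and makes the loss conditional.

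**Blood pressure is not established.** A reader might extend the point to BP outlier counts. Only the ECG outlier table is expressly by visit. SAP 6.3.4 windows only what is summarized by visit, so 6.3.5 need not govern the vital-sign outlier table. This stands: for vital signs the defect is an ambiguity.

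**Protocol 8.6 is narrower than it looks.** It commits to whole-period summaries for unscheduled categorical data, with ECG finding categories as its example. Unscheduled quantitative values are to be listed only, so it gives no clear support for counting unscheduled BP or raw QTcF. Whether a QTcF value cut at a threshold is categorical is not stated. This stands, but it exposes two mismatches: the visible SAP carries forward no whole-period summary for C-SSRS or ECG categories, and SAP 6.3.4 lets unscheduled quantitative values into by-visit summaries.

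**Findings are still reported elsewhere.** Listings remain. Protocol 7.2 requires abnormal assessments with signs or symptoms, or judged clinically significant, to be recorded as AEs. Supine hypertension and cardiac arrhythmia are events of special interest queried at each visit (protocol 7.1.4). SAP 9.1 tabulates TEAEs by arm without visit windows. This stands in part. Listings give no per-arm count, and the AE route depends on symptoms or investigator judgment, so an asymptomatic QTcF crossing may not reach it.

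**Averaging a yes/no item** has no meaning, but it arises only when two records share a date and time, so it is a minor gap.

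**Conclusion.** The point holds for C-SSRS and for ECG outliers on study days 15–42. Followed exactly, the visible SAP can omit a positive form or a QTcF outlier from the relevant table, and no any-time row recovers it. The effect on the overall count is never upward.

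The documents do not determine the size. They give no frequency of unscheduled visits, which only may include these assessments. The percentages in step 6 rest on assumed timing, do not describe the ECG window, and count records rather than positive findings.

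A reader might also infer a bias between arms. That requires one arm to have more safety-driven visits or more unselected positives, and nothing in the documents shows this.

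SAP Appendix 1 (listed in the contents as changes to protocol-planned analyses) and Section 9.1.1 are redacted, so an exception there cannot be excluded. Subject to that, the SAP should be changed. Efficacy analyses and type I error are not affected.

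**What to change.** 1. State in SAP 6.3.5 that the selection rule applies to by-visit summaries only. Keep it for means and changes from baseline.
2. Add one row per arm, any time after first dose (worst category per subject), to the C-SSRS and ECG outlier tables. Use all scheduled, unscheduled, ET and Visit 7 records, and exclude data after entry to Study 0170, in line with the AE rule in SAP 9.1. This row also recovers ECGs before study day 15 and Visit 7 C-SSRS forms that Table 3 leaves without a window.
3. State in SAP 9.5 that the vital-sign outlier table is handled the same way.
4. Reconcile this with protocol 8.6: say whether thresholded values count as categorical, and whether unscheduled quantitative values enter by-visit summaries.

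The cost is SAP wording and a few table rows. Outlier percentages will rise slightly, and subjects with more visits have more chances to be counted. A table footnote should say so.

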7. STUDY POPULATION

7.1. Enrollment by Investigator

Enrollment by geographic region (North America, Europe, Asia/Pacific, and Other), country, and investigator will be summarized overall and by treatment group for all randomized subjects.

7.2. Subject Disposition and Completion Status

Subject disposition will be summarized for all randomized subjects by treatment group. The summary will include the counts and percentages of subjects in each analysis set as well as of subjects who:

- Were randomized and treated with study drug
- Were randomized and not treated with study drug
- Completed the 4-week treatment period
- Didn't complete the 4-week treatment period and the reason for not completing it (adverse event, loss of follow-up, noncompliance with study drug, physician decision, pregnancy, protocol violation, study terminated by Sponsor, and other)
- Completed the study
- Didn't complete the study and the reason (adverse event, loss of follow-up, noncompliance with study drug, physician decision, pregnancy, protocol violation, study terminated by Sponsor, and other)
- Continued to Study 0170
- Didn't continue to Study 0170 and the reason (did not complete study, chose not to continue, and other)

A listing of subject disposition will include the FAS status, the date of informed consent signed, the date of first dose and last dose of study drug, the primary reason for discontinuation of study treatment, the date of last visit, the study completion status, the primary reason for study termination, and the date of last contact.

7.3. Protocol Deviations

FAS subjects reporting major protocol deviations will be summarized overall and by treatment group. The summary will include counts and percentages of subjects who have any major PDs and counts and percentages of subjects who have major PDs in each category. A separate summary table will be provided for COVID-19 related PDs.

A subject listing with all protocol deviations identified prior to database lock will be provided. All subject listings will be based on the randomized analysis set.

7.4. Medical History and Medical Conditions Present at Entry

Medical history will be summarized by system organ class and preferred term, overall and by treatment group, for the safety analysis set. No statistical comparisons will be performed.

Medical history will be mapped according to [REDACTED].

7.5. Demographic and Baseline Clinical Characteristics

A summary of demographic and baseline characteristics will include the following items: age (years), age category (<65 years, ≥65 years), sex, race, ethnicity, weight (kg), height (cm), BMI (kg/m²), smoking status (Never, Current, Former, Missing), Diagnosis of Primary Autonomic Failure (Multiple System Atrophy, Parkinson's Disease, Pure Autonomic Failure), OHSA#1 score, OHSA composite score, OHDAS composite score, OHQ overall composite score, Supine SBP (mmHg, an average of 5 min and 10 min measurements), 3 min Standing SBP (mmHg), and norepinephrine (NE) (pg/mL).

This summary will be presented for the safety analysis set, FAS, and PP analysis set.

8. EFFICACY

8.1. General Considerations

For all efficacy data analyses, the FAS will be used unless otherwise specified.

Nominal p-values (i.e., unadjusted for multiple testing) will be provided as appropriate.

If a statistically significant treatment effect on the primary efficacy endpoint has been demonstrated, secondary efficacy endpoints will be tested in a hierarchical fashion using 2-sided tests at the 5% level of significance until a failure to reject the null hypothesis occurs.

8.2. Statement of the Null and Alternative Hypotheses for the Primary Endpoint

The primary endpoint, the change from baseline in OHSA#1 (dizziness, lightheadedness, feeling faint or feeling like blacking out) at Week 4, is used to evaluate the effectiveness of TD-9855 (amprelosetine) therapy relative to the placebo.

The null hypothesis for the treatment comparison is that there is no difference between amprelosetine (TD-9855) (active) group and the placebo group in the mean change in OHSA#1 from baseline at Week 4. The alternative hypothesis is that there is a difference. The hypothesis testing schema is expressed as follows:

$$H_0 : \mu_{Active} = \mu_{placebo}$$

$$H_1 : \mu_{Active} \neq \mu_{placebo}$$

where μ stands for the mean change from baseline at Week 4.

8.3. Analysis of the Primary Efficacy Endpoint

8.3.1. Primary Efficacy Analysis

A mixed effects model for repeated measures (MMRM) incorporating the change from baseline in OHSA#1 as the dependent variable will be used to assess the primary endpoint hypothesis.

The model will include fixed class terms for treatment group and baseline disease type (MSA, PD, PAF), a covariate for baseline OHSA#1 score, and a time effect (week) and its interaction terms with treatment and baseline OHSA#1 score. An unstructured covariance structure (type=UN) to account for the repeated measures within a subject will be fitted. If the model doesn't converge, the data will be reanalyzed fitting a compound symmetric covariance structure (type=CS) and a compound symmetric with heterogenous variance covariance structure (type=CSH) and the structure with a lower AIC value will be selected.

Least squares (LS) mean change in OHSA#1 in each treatment group and the difference in LS mean change between treatment groups will be estimated. Point estimates, 95% confidence intervals (CIs), and p-values will be provided.

Figures

A plot will present the LS mean change from baseline in OHSA#1 at each postbaseline time point by treatment group with 95% CIs.

8.3.2. Sensitivity and Supplementary Analyses for Primary Efficacy Endpoint

A sensitivity analysis is planned to evaluate the sensitivity of the primary efficacy analysis results to the assumption that missing data are missing at random (MAR). A supplementary per protocol analysis will be performed.

8.3.2.1. Per Protocol Analysis

The per protocol analysis follows the same MMRM method described in Section 8.3.1 and is restricted to subjects in the PP analysis set.

8.3.2.2. Tipping Point Analysis

The tipping-point analysis will be conducted for the primary efficacy endpoint, change in OHSA#1 at Week 4, to evaluate the robustness against deviation from the missing at random (MAR) assumption using MMRM. The tipping-point analysis refers to imputing the missing data with a range of scenarios to identify the tipping point at which the imputation overturns the significance of the treatment effect under MAR assumption. The tipping point is determined as the minimum shift value to overturn the significant results of the multiple imputation (MI) when the shift value is added to the Week 4 imputed values for active group subjects. If the tipping point is implausibly large, it is concluded that the study results are not sensitive to the MAR assumption.

For the tipping point analysis, the MMRM model as specified for the primary efficacy analysis will be fitted. The initial results obtained when no shift is applied to active group Week 4 imputed values will be provided, along with the minimum shift that overturns the significant result.

